All patients will receive a neuraxial technique in the sitting position at L3/4 or L4/5 using loss of resistance to saline. In the DPE group, a 25-g Whitacre needle will be used to puncture the dura. In both groups, the epidural catheter will be threaded 5 cm in the epidural space with an initiation dose of 15 ml of ropivacaine 0.1% with fentanyl (2 mcg/ml) over 6 minutes as per standard practice. Labor analgesia will be maintained by programmed intermittent bolus with 6 ml of the same solution every 45 minutes starting 30 minutes after the initial dose. Patients will have patient-controlled epidural analgesia (PCEA) available with an 8 ml dose per demand, every 10 minutes, for a maximum dose of 45 ml for every hour.

Assignment of Study Cohorts:

Study participants will be randomized by computer-generated sequence to EPL or DPE arms, stratified by class of obesity (BMI \geq 35<40 kg/m², \geq 40<50 kg/m² and \geq 50 kg/m²) and by parity (nulliparous versus multiparous). Patients will be assigned to one of the four study arms by computer-generated, randomized sequence in order to balance baseline characteristics across the arms. This will be a double-blinded study. After the consented and enrolled participant

requests labor epidural, a study member will give the anesthesia provider a sealed envelope with study assignment for either standard EPL or DPE technique.

Protocol for Breakthrough Pain

- If the patient has uneven or unilateral level, the provider will withdrawal catheter 1cm from skin and bolus 5ml of epidural mix. As fetal heart rate allows for maternal repositioning, the patient will lay lateral position with unblocked side in the dependent position. (up to 3 catheter adjustments)
- If the patient has bilateral levels at that below T10 to ice, the patient will be administered 5 ml off epidural pump, up to 3 times in 15 minutes.
- If the patient has pain despite T10 levels, the provider will administer Fentanyl 100 mcg via epidural.
- If analgesia continues despite these interventions up to 3 times within 60 minutes, the attending anesthesiologist will determine if epidural catheter needs replacement.

Data analysis and monitoring:

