The primary outcome of this study is block quality which will be defined by a composite of five components (1) asymmetric block after 30 minutes of initiation, (2) top-up interventions, (3) catheter adjustments (4) failed catheter requiring replacement, and (5) failed epidural requiring general anesthesia or replacement neuraxial anesthesia for emergency cesarean section. The composite outcome is a practical endpoint for our study because while necessary to determine block quality, incidence of failed epidural or one-sided epidurals are rare. All five components are of similar importance when assessing the quality of epidural analgesia. Therefore, this outcome definition will increase the power of the study, without sacrificing clinical relevance or feasibility.

Block level will be measured by temperature discrimination with ice, and levels that are greater than two dermatomal levels would be considered asymmetric. Lower extremity dermatomal levels will be assessed by stimulating the inguinal crease (L1), anterior thigh (L2), medial knee (L3), medial malleolus (L4), between the great and second toe (L5), the lateral heel (S1), and the medial popliteal fossa (S2). On the thoracic levels, the torso will be assessed bilaterally at the mid-clavicular line.

Secondary outcomes include time to numeric pain rating scale ≤1, maternal adverse events (hypotension, fetal bradycardia, PDPH), motor block, duration of second stage of labor, total labor epidural time, total anesthetic dose required, PCEA use, and mode of delivery.

Statistical Methods:

The primary assessment of difference in the composite outcome between the two epidural techniques will be conducted via chi-square test. Using data from a recent retrospective study on labor maintenance regimens published by our group, we expect the composite event rate to be 35% in the group receiving EPL.¹⁷ Based on the findings by Hess *et al.* of a 62% relative reduction in breakthrough pain with a CSE technique compared to an EPL, we will define a clinically meaningful effect in our study as a similar reduction in the composite outcome to be 14% in the DPE group, which corresponds to an odds ratio of $0.30.^{18}$ A two-sided χ^2 test for the difference in composite outcome rates between epidural techniques at alpha level 0.05 will reach 80% power to detect an odds ratio of 0.30 comparing DPE to EPL in a study of 130 patients (65 DPE and 65 EPL).

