Further analysis of the difference in the composite outcome between the two epidural techniques will be conducted via multivariate logistic regression to account for potential confounders. Comparison of additional secondary outcomes between the epidural techniques of

maternal adverse events, total labor epidural time, total anesthetic dose required, mode of delivery, and degree of motor block will be compared with χ^2 tests and logistic regression. The time to numeric pain rating scale ≤ 1 will be compared between the two epidural techniques via Kaplan-Meier estimates and log-rank tests.

Data will be monitored closely for the occurrence of adverse events (AE) and reported to the IRB as needed. If unanticipated AEs or if expected events appear to be occurring more frequently than expected, those AEs will be explored per treatment arm.

In accordance with federal regulations, the PI will monitor for, review, and promptly report to the IRB, appropriate institutional officials, sponsor, coordinating center and the appropriate regulatory agency head all unanticipated problems involving risks to subjects or others that occur in the course of a subject's participation in a research study (45 CFR 46.103(b)(5)(i) and 21 CFR 56.108(b)(1)), all AE reports will be reported per the DUHS IRB policies.

Data storage and confidentiality:

Study records will remain confidential as required by law. Federal Privacy regulations ensure privacy, security and authorized access. Patient identifiers including but not limited to name, social security number, address, and telephone number will not be disclosed outside of the Duke University Health System (DUHS). For records shared with parties outside of DUHS, patients will receive a unique code number. The key to the code will be kept in a locked file in [name] office.

Risk/benefit assessment:

The will be no benefit to subjects from participating in the study, since standard of care regimens will be used in this study. The information gained from the study will help elucidate if

DPE offers benefits over standard EPL for initiation and maintenance of labor analysis in our practice. Risks of epidural analysis are the same irrespective of participation in the study. These are 1.5% rate of unintentional dural puncture with epidural needle, <1% risk of post-dural pucture headache, inadequate analysis, and unintentional intravascular or subarachnoid injection. ^{19,20}

References:

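### Total anesthetic dose is compared with no scaling to time, although both arms receive the same programmed 8 ml/h, so this secondary outcome is insensitive to technique

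*Combined protocol and SAP*

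**What the plan says.** **Outcomes.** Under *Data analysis and monitoring*, the secondary outcomes end with "total labor epidural time, total anesthetic dose required, PCEA use, and mode of delivery". None of these is defined further. Epidural time is an outcome in its own right and is not used as a denominator for dose.

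**Dosing.** Under *Epidural technique*, both groups receive "an initiation dose of 15 ml of ropivacaine 0.1% with fentanyl (2 mcg/ml) over 6 minutes as per standard practice", followed by "programmed intermittent bolus with 6 ml of the same solution every 45 minutes starting 30 minutes after the initial dose". Two components can respond to the quality of the block:

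- PCEA, "with an 8 ml dose per demand, every 10 minutes, for a maximum dose of 45 ml for every hour"
- clinician doses under *Protocol for Breakthrough Pain*, for example "the patient will be administered 5 ml off epidural pump, up to 3 times in 15 minutes"

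**Analysis.** Under *Statistical Methods*, "total anesthetic dose required, mode of delivery, and degree of motor block will be compared with χ^2 tests and logistic regression". No rate, offset or duration term is mentioned. The adjusted logistic regression described just before this is for the primary composite. PCEA use does not appear in that section, so no analysis is stated for it.

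**The concern.** The outcome is worded as the dose required, which reads as a measure of analgesic need. The initiation dose and the programmed boluses are set by the protocol, not by need, and the programmed boluses accumulate with time. Wide variation in epidural duration should be expected, because the trial enrolls nulliparous and multiparous women in spontaneous or induced labor at 2-7 cm dilation.

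A woman with a perfect block and a long labor can therefore record a larger total than a woman with a poor block who delivers early. At stake is sensitivity: if DPE really lowers analgesic need, variation in labor length may hide it, and a null result on total dose could be misread as evidence that the techniques are equivalent on this point.

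**Working it through.** **1. The plan's own figure.** The only power statement concerns the primary composite: "A two-sided χ^2 test for the difference in composite outcome rates between epidural techniques at alpha level 0.05 will reach 80% power". With 35% against 14%, 65 per arm and pooled proportion 0.245:

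z = (0.21·√65 − 1.96·√(2·0.245·0.755)) / √(0.35·0.65 + 0.14·0.86) = (1.693 − 1.192)/0.590 = 0.85

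This gives power of 0.80, so the figure reproduces. It does not use dose. The documents state no figure for dose or PCEA use.

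**2. The fixed part, from the protocol's figures.** Programmed rate: 6 ml / 0.75 h = 8 ml/h. Programmed volume by time T in minutes: 6 × (floor((T − 30)/45) + 1).

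| Epidural time | Programmed | With initiation |
|---|---|---|
| 3 h | 4 × 6 = 24 ml | 39 ml |
| 8 h | 11 × 6 = 66 ml | 81 ml |
| 15 h | 20 × 6 = 120 ml | 135 ml |

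A woman at 3 h would need (135 − 39)/8 = 12 PCEA demands to match the total of a woman at 15 h who made none.

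**3. The share of the total (demand rate assumed).** At 8 h the share is 81/(81 + 64 × demands per hour): 72% at 0.5 demands/h, 56% at 1 and 39% at 2. It falls below half above 81/64 = 1.27 demands/h. For epidurals of 4-16 h that threshold lies at about 1.1-1.4 demands/h.

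**4. Why time matters.** Write r for a woman's demand rate in ml/h and T now in hours. Approximately, total = 15 + (8 + r)·T, so (total − 15)/T = 8 + r. Dividing by time removes the variation in T and leaves the part that technique can change.

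Hand check (assumed: mean 8 h, SD 4 h, r = 6 ml/h on EPL, CV 0.7, reduction 1.5-2 ml/h, EPL spread used for both arms):

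- Raw total: SD from duration alone is (8 + 6) × 4 = 56 ml. SE of the difference is 56·√(2/65) = 9.8 ml. The expected difference is 12-16 ml, or 1.2-1.6 SE, before any between-woman variation in demand.
- Per hour: SD is 0.7 × 6 = 4.2 ml/h. SE is 4.2·√(2/65) = 0.74 ml/h. A difference of 1.5-2 ml/h is 2.0-2.7 SE.

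**5. Simulated power (all inputs assumed).** Lognormal duration, mean 6-10 h, with the SD rising with the mean from 3 to 6 h; gamma demand rate independent of duration, 4-8 ml/h on EPL; reduction 1.5-2 ml/h; CV 0.6-0.8; 65 per arm; Welch test at two-sided 0.05.

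- Raw total: power about 11-49%.
- Per hour, without the initiation dose: about 29-100%, and higher in every scenario.
- Duration explains about 55-87% of the variance in the raw total.

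The raw-total range depends on pairing larger SDs with larger means. Crossing means and SDs freely widens it (a 10 h mean with only a 3 h SD is kinder to the raw total), but the hourly form still had the higher power throughout.

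**6. A second set of assumptions.** Mean 8 h, SD 4 h, demand rate lowered by 30%, 65 per arm; the hourly total here still includes the initiation dose.

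| EPL demands/h | Raw total | Total per hour | Raw PCEA ml | PCEA ml per hour |
|---|---|---|---|---|
| 0.5 | 17% | 46% | 39% | 50% |
| 1 | 31% | 67% | 52% | 69% |
| 2 | 46% | 84% | 62% | 85% |

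At 1 demand/h, the R² of dose on duration falls from 0.57 (raw) to 0.02 (per hour). For mean durations of 6-10 h with the SD at half the mean, duration explains 15-34% of the variance in raw PCEA volume, through exposure time alone.

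**The case against.** **Total dose is a legitimate quantity.** It measures cumulative drug exposure, and epidural time is reported beside it. Duration arises after randomization, so if technique altered labor length, dividing by duration could hide a real difference in exposure. This stands. It is the reason to keep the raw total, not a reason to use it as the measure of need.

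**Randomization protects the comparison.** Allocation is stratified by parity and BMI class, and chance imbalance in labor length is ordinary sampling error covered by alpha. This also stands. A reader might infer that the dose comparison is biased; the documents do not support that unless technique changes labor length. The loss is of precision.

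**The programmed dose may not dominate.** A reader might infer that most of the total is programmed. The documents give no demand rate and allow up to 45 ml/h of PCEA, at which the programmed part is 8/53 = 15% of hourly volume, or 8/45 = 18% if the ceiling includes it. Under the assumptions of step 5 the programmed part alone is about 43-59% of EPL volume, and the initiation dose, though identical in both arms, does not grow with time. A majority is therefore not established. It is not needed either: at 2 demands/h the fixed share is 39% and the hourly form still gains (46% to 84%).

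**PCEA use is a different case.** It contains no programmed dose, so that mechanism cannot be carried over to it. It has no unit and no stated analysis, and could mean yes/no, a count or a volume. Only if it is a raw volume does it depend on duration, and then less strongly.

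**The test is the more visible fault.** Chi-square and logistic regression do not suit a continuous dose. That is so, but if the dose were dichotomized to fit them, a cutoff on the total would still largely sort women by duration.

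**Conclusion.** The point holds as a matter of sensitivity. The identical regimen, the absence of any time scaling and the separate collection of epidural time are all in the text. The size is not: durations, demand rates and effects are assumptions. Under those of step 5, power is about 11-49% on the raw total against about 29-100% per hour. The direction is consistent, but the hourly form is no guarantee: with demand of 8 ml/h and a reduction of 1.5 ml/h, its power is only about 29-50%.

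The point is limited to secondary outcomes with no power claim attached. A reader might infer that the main result is weakened; it is not, because the composite does not use dose and already counts top-ups and catheter adjustments directly.

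**What to change.** Under *Data analysis and monitoring* and *Statistical Methods*:

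- Define (a) epidural dose per hour of labor epidural time, excluding the initiation dose.
- Define (b) PCEA volume per hour, adding clinician-administered boluses where their volumes are recorded, and name it as the measure of analgesic requirement.
- Replace the chi-square test for these outcomes with a method for continuous data, such as a rank-based test or a model with epidural duration as an offset, and state an analysis for PCEA use.
- Report the raw total and total labor epidural time beside them, by arm.

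The cost is mostly wording. Epidural time is already an outcome, but the documents do not say that PCEA, programmed and clinician volumes are recorded separately, so this should be confirmed before (b) is fixed. Hourly rates are noisy in very short labors; medians or the offset model limit this. No dosing rule and no sample size changes.

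### PDPH, analysed on its own at the protocol's rate of under 1%, will usually yield no finite logistic odds ratio; plan by-arm counts and a risk difference with a score or exact interval

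*Combined protocol and SAP*

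**What the plan says.** Under Data analysis and monitoring, the secondary outcomes include "maternal adverse events (hypotension, fetal bradycardia, PDPH", among others. The Statistical Methods section then gives one analysis for a group of secondary outcomes that contains these events: "maternal adverse events, total labor epidural time, total anesthetic dose required, mode of delivery, and degree of motor block will be compared with" chi-square tests and logistic regression. It does not say whether the three events are analysed singly or pooled. It names no exact test, no penalised model, no interval and no fallback for sparse data.

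The Risk/benefit assessment puts PDPH at "<1% risk of post-dural pucture headache", as a general risk of epidural analgesia rather than a figure for each technique. The sample size is set for the primary composite, "in a study of 130 patients (65 DPE and 65 EPL".

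**The concern.** Both named methods rely on large samples, and by the protocol's own figure PDPH would give fewer than 65 × 0.01 = 0.65 expected events per arm. When one arm has no event, the maximum-likelihood odds ratio from logistic regression is zero or infinite. When neither arm has one, the Pearson chi-square statistic is 0/0.

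Under Epidural technique, the DPE arm adds a deliberate dural puncture, so PDPH is a harm tied directly to the experimental step. At this sample size no test can say much about it. The useful statement is how large a difference the data still allow, and the plan does not ask for that. A non-significant p-value reported without an interval could be misread as reassurance.

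**Working it through.** **Inputs.** n = 65 per arm (Statistical Methods). PDPH rate p ≤ 0.01 (Risk/benefit assessment), applied to both arms as an assumption. The documents give no rate for hypotension or fetal bradycardia, and no figure for the adverse-event analysis.

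**The plan's own figure first.** The stated power claim is for the primary composite, at 35% v 14% and two-sided alpha 0.05. With mean rate 0.245,

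n = [1.96·√(2·0.245·0.755) + 0.842·√(0.35·0.65 + 0.14·0.86)]² / 0.21² ≈ 65 per arm.

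Power at 65 per arm is 80.2%, and the odds ratio is (0.14/0.86)/(0.35/0.65) = 0.302. The primary sample size reproduces and is not in question here.

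**Zero-event arms for PDPH.** With q = (1 − p)^65 the chance that an arm has no event:
- at least one arm empty, so no finite logistic odds ratio: 1 − (1 − q_EPL)(1 − q_DPE)
- both arms empty, so chi-square undefined as well: q_EPL × q_DPE

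At 1% in both arms, q = 0.99^65 = 0.520. At least one arm is empty with probability 1 − 0.480² = 0.770, and both with probability 0.520² = 0.271. Exactly one is empty in 0.770 − 0.271 = 0.499.

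| EPL rate | DPE rate | At least one arm empty | Both arms empty |
|---|---|---|---|
| 1% | 1% | 77.0% | 27.1% |
| 0.5% | 0.5% | 92.3% | 52.1% |
| 1% | 2% (assumed) | 64.9% | 14.0% |
| 1% | 3% (assumed) | 58.7% | 7.2% |
| 1% | 5% (assumed) | 53.7% | 1.9% |
| 5% (assumed) | 5% (assumed) | 7.0% | 0.1% |
| 10% (assumed) | 10% (assumed) | 0.2% | about 0% |

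The first two rows apply the protocol's ceiling, and half of it, to both arms. The last two show how quickly the difficulty fades for a commoner event.

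**Behaviour of the tests.** These figures come from summing binomial probabilities over all tables that reject at two-sided 0.05. Uncorrected chi-square rejects in 0.4% of trials at 1% v 1% and in 7.0% at 1% v 3%. Fisher's exact test rejects in 0.005% and 0.7%. The choice of test can decide the label: 4 events v 0 gives p = 0.042 by chi-square and p = 0.119 by Fisher.

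**What an interval still gives.** After 0/65, the exact upper 97.5% limit for one arm is 1 − 0.025^(1/65) = 5.5%. For 0/65 v 0/65, the score limit is z²/(n + z²) = 3.84/68.84 = 5.6%, so the 95% interval for the risk difference is about −5.6 to +5.6 percentage points. This is the table in which both planned methods fail.

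**The case against.** A reader might infer that the planned analysis gives no usable answer for adverse events. The documents do not support that, for three reasons.

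- **Chi-square is also named.** It fails only when both arms are empty. At 1% in both arms it returns a p-value in the other 73% of trials, and it does not over-reject there.
- **The figures cover PDPH only.** No rate is given for hypotension or fetal bradycardia, and at an assumed 5% or more an empty arm is uncommon. Pooling the events could also remove the numerical failure, and the text does not rule pooling out, although it would hide PDPH among different harms.
- **The 77% needs both arms at or below 1%.** A higher DPE rate lowers it.

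It can also be said that an empty arm does not make the likelihood uninformative. With 1/65 under EPL and 0/65 under DPE, a profile-likelihood interval from the same logistic model bounds the DPE odds ratio above at 5.8; with 2/65 v 0/65 the bound is 1.6. This is correct, but the plan specifies no such interval. The upper bound is also lost when EPL is the empty arm, which is the case that matters if DPE causes headaches.

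Finally, replacing chi-square by Fisher would cost power and repair no error-rate problem. That stands, and it is why the interval, not another test, should be the main output. The plan does provide for exploring adverse events by arm if they exceed expectation, but this sets no method and depends on a trigger.

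**Conclusion.** The point holds for PDPH analysed on its own. At 1% or less in both arms, the planned logistic regression has no finite treatment odds ratio in at least 77% of trials, and chi-square is undefined in at least 27%. At an assumed 1% v 3%, an empty arm still occurs in 59%.

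These results rest on 65 analysed women per arm, on PDPH not being pooled with other events, and, for the 77% and 27%, on applying the protocol's unsplit figure to both arms. The loss is of an effect estimate and a bound on harm, not of error control. This is a minor, cheaply corrected weakness in a secondary safety analysis, with no bearing on the primary comparison.

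**What to change.** Add one or two sentences to Statistical Methods:

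- Analyse hypotension, fetal bradycardia and PDPH separately.
- For PDPH, and for any other event with fewer than 5 expected per arm, make counts by arm and a risk difference with a score or exact 95% confidence interval the main output, in place of the logistic odds ratio. Name the interval method in advance.
- If a p-value is wanted, use an unconditional exact test rather than Fisher's, which is much more conservative here.
- If a model is wanted, use Firth-penalised logistic regression.

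The cost is slightly more analysis work and a wide interval, which describes fairly what 65 women per arm can show. Sample size, conduct and the primary analysis do not change.

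### Total labor epidural time and total anesthetic dose are quantitative, but the plan assigns them chi-square tests and logistic regression without categories and names no continuous-outcome method

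*Combined protocol and SAP*

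**What the plan says.** The secondary outcomes are listed under Data analysis and monitoring. After time to a pain score of 1 or less and maternal adverse events, the list reads "motor block, duration of second stage of labor, total labor epidural time, total anesthetic dose required, PCEA use, and mode of delivery".

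Statistical Methods then gives two rules for secondary outcomes. One sentence takes maternal adverse events together with four others, and pairs the chi-square test with logistic regression for all five: "total labor epidural time, total anesthetic dose required, mode of delivery, and degree of motor block will be compared with χ^2 tests". The next takes time to pain score ≤1, which "will be compared between the two epidural techniques via Kaplan-Meier estimates and log-rank tests". Second-stage duration and PCEA use are not mentioned there.

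The Epidural technique section shows what total dose consists of: a 15 ml initiation dose, then "programmed intermittent bolus with 6 ml of the same solution every 45 minutes starting 30 minutes after the initial dose", plus patient-controlled analgesia "available with an 8 ml dose per demand, every 10 minutes".

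Under Assignment of Study Cohorts, randomisation is "stratified by class of obesity" (three BMI bands) and by parity.

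**The concern.** The grouped sentence suits mode of delivery and adverse events, which are categorical. It does not suit a duration in minutes or a volume in ml. To apply the stated methods to those, someone must first choose cut-points, and the plan gives none.

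Two things are lost even if the cut-points are chosen with care. Dichotomising discards information, so a real difference is more likely to be missed. The result is also a difference in proportions or an odds ratio around an arbitrary threshold, when the useful answer is how many minutes or ml separate the techniques. And two analysts working from this text could choose different categories and report different results.

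**Working it through.** **1. Match outcomes to methods.**

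| Secondary outcome | Type | Method in Statistical Methods |
|---|---|---|
| Time to pain score ≤1 | time to event | Kaplan-Meier, log-rank |
| Maternal adverse events | binary | chi-square, logistic |
| Mode of delivery | categorical | chi-square, logistic |
| Motor block | scale not stated | chi-square, logistic |
| Total labor epidural time | duration | chi-square, logistic; no categories |
| Total anesthetic dose | volume | chi-square, logistic; no categories |
| Second-stage duration | duration | none |
| PCEA use | not defined | none |

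Six of the eight outcomes have a method. Two of those six are quantitative outcomes with a categorical method, and two of the eight have no method.

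**2. Confirm that dose is a quantity.** With boluses at 30, 75, 120, … minutes, programmed volume at an assumed 4 h is 15 + 5 × 6 = 45 ml, and at an assumed 12 h it is 15 + 16 × 6 = 111 ml. The gap is 66 ml, about eight PCEA demands (66 / 8 = 8.25). These two totals are the same whether the 30 minutes runs from the start or the end of the 6-minute initiation dose.

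**3. Reproduce the plan's own figure.** Inputs from Statistical Methods: 35% versus 14%, two-sided alpha 0.05, 80% power. The mean rate is (0.35 + 0.14)/2 = 0.245.

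n per arm = [1.960 × √(2 × 0.245 × 0.755) + 0.842 × √(0.35 × 0.65 + 0.14 × 0.86)]² / (0.35 − 0.14)² = (1.192 + 0.496)² / 0.0441 ≈ 64.6, so 65.

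This matches 65 per arm and 130 in total; power at 65 is 80.2%. Nothing below alters it.

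**4. Illustrate what categorising costs.** Assumptions, none from the documents: normal data, equal SDs, a shift of 0.5 SD. Taken from the plan: 65 per arm. The two-sided 0.05 level is the plan's level for the primary test, carried over here.

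- *Comparison of means.* 0.5 × √(65/2) = 2.850, and Φ(2.850 − 1.960) = Φ(0.890) = 81.3%. By simulation the t-test gives 80.8%.
- *Wilcoxon.* 78.9% by simulation.
- *Chi-square at a pre-set cut midway between the arms.* The proportions above the cut are Φ(0.25) = 0.599 and Φ(−0.25) = 0.401. The normal approximation gives 61.7%; exact enumeration gives 60.0%.
- *Chi-square at the pooled sample median.* 56.2% by simulation. This cut is known only once the data are in, so it is not a pre-set cut.
- *Chi-square on four quartile groups (3 df).* 56.9% by simulation.

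The loss is about 81 − 60 = 21 points for the pre-set cut and 81 − 56 = 25 points for the sample-median split.

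**5. Range.** By normal approximation, over shifts of 0.4 to 0.6 SD, power runs from 63% to 93% for means and from 44% to 77% for a pre-set central cut. At 0.4 SD, simulation gives 61.9% (t-test), 59.8% (Wilcoxon) and 38.6% (sample-median split).

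**The case against.** The strongest defence is that this is loose drafting. One sentence sweeps up five outcomes, the methods fit some of them, and a competent analyst handed minutes and ml would use a continuous method anyway. No secondary outcome is powered. That limits the weight of the point, but the text still states a method and the method does not fit. The plan does match method to data type for time to pain relief.

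Logistic regression could also be ordinal, which needs no cut-points and whose score test is equivalent to Wilcoxon, so it would lose little. The plan does not name that model, and the only logistic model it describes further is for the binary composite. An ordinal model would also leave the chi-square test without categories.

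Three stronger readings are tempting, and the documents do not support them.

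- *That the false-positive rate is inflated.* Taking the best of three quartile cuts after seeing the data would reject a true null 10% to 14% of the time. But the plan does not call for searching cut-points. It only fails to rule this out.
- *That total dose is an invalid outcome because it grows with labor length.* The arms are randomised, so a difference in total dose is a valid effect of technique even if part of it acts through duration. Dose per hour is a different estimand and divides by epidural time, itself a post-randomisation outcome.
- *That the trial's main result is compromised.* The composite is binary, chi-square suits it, and the sample size reproduces.

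**Conclusion.** The point holds for total labor epidural time and total anesthetic dose: the stated methods do not suit them as measured, and no suitable method is given elsewhere. If the text is followed, the plausible cost is 20 to 25 percentage points of power at a moderate difference, and no estimate in minutes or ml. The power figures rest on assumed normal data and an assumed 0.5 SD shift. The mismatch itself does not depend on them.

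The absent methods for second-stage duration and PCEA use, and the undefined PCEA outcome, are missing detail and weigh less. This should be fixed, but it reaches secondary outcomes only.

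**What to change.** In Statistical Methods, take total labor epidural time and total anesthetic dose out of the chi-square sentence and state:

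- Both are compared as continuous outcomes, either by linear regression adjusted for the stratification factors BMI class and parity, with the scale (original or log) fixed before unblinding, or by a Wilcoxon test. Choose one in advance. Report the difference or ratio with a 95% confidence interval.
- Chi-square and logistic regression remain for mode of delivery and binary adverse events.
- Second-stage duration uses the same continuous method, labelled as restricted to women who reach second stage, because that group is formed after randomisation.
- PCEA use is defined as any use, number of demands or volume. Any use takes chi-square or logistic regression; demands or volume take the continuous method.

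Dose per hour of epidural time may be added as a descriptive summary, but it is optional and should not replace total dose.

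The cost is a few rewritten lines and one definition. Epidural time, dose, second-stage duration and PCEA use are already listed outcomes, and BMI class and parity are already needed for randomisation, so no extra patients are required and no new measurement should be. The primary analysis and N = 130 are unchanged.
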